6.1.1 Induction Therapy: Week 0 to Week 12 (Last Dose at Week 10)

Double-blind Induction Therapy is separated into Part A for administration of multiple ascending IV doses of KHK4083 (or placebo) to subjects in Cohorts 1 - 3 and Part B for administration of the recommended IV dose (one of three dose levels identified in Part A) of KHK4083 (or placebo) to subjects in Cohort 4. Subjects in Part A are prohibited from participating in Part B.

Subjects in each cohort will be randomly assigned in a 3:1 ratio to receive KHK4083 or placebo by IV infusion over 60 minutes (\pm 10 minutes). Each subject will receive a total of 6 treatments (one IV infusion per treatment) every 2 weeks from Week 0 (Day 1) to Week 10 of Induction Therapy. Safety assessments (e.g., after 2 treatments for 1.0 mg/kg and 3 treatments for 3.0 and 10 mg/kg are administered and 14-day safety data from the last treatment are available) will determine whether dosing will continue for subjects within a cohort and if the investigational product will be administered at the next higher dose level for subjects in the next cohort in Part A or for Cohort 4 in Part B (refer to Section 6.3 for details on the Safety Monitoring Plan).

For subjects in all cohorts, a sigmoidoscopy with biopsy is scheduled at Week 12 to assess improvement in the mucosa from Baseline (Week 0) to Week 12. It is highly recommended that the sigmoidoscopy with biopsy be performed within 7 to 13 days prior to the Week 12 visit. The sigmoidoscopy results from the central reader are required before a subject receives treatment in the OLE/LTE Therapy phase.

6.1.2 Long-term Extension Therapy: Week 12 (First Dose) to Week 52

The LTE is only active for subjects who entered it prior to approval of Amendment 2. Subjects who sign an ICF under Amendment 2 are eligible for the OLE (see Section 6.1.3).

Subjects who completed double-blind Induction Therapy (i.e., at least five of six treatments) and had a clinical response or mucosal healing were eligible to continue in double-blind LTE Therapy. A clinical response is defined as a reduction in the total Mayo Clinic score of at least 3 points and a decrease of at least 30% from Baseline (Week 0) to Week 12, and a reduction in the rectal bleeding subscale of at least 1 point from Baseline (Week 0) to Week 12 or an absolute rectal bleeding score of 0 or 1 at Week 12. Mucosal healing is defined as a mMES of 0 or 1.

All subjects who qualified were to have been given two options:

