- 1) To receive no further treatment and proceed directly to the Induction Therapy Follow-up Period (Week 16 through Week 26); or
- 2) To continue in double-blind LTE Therapy and receive 10 additional treatments of KHK4083 (at the same dose administered to that subject during Induction Therapy) or placebo as maintenance therapy. Each subject will receive one IV infusion every 4 weeks from Week 12 to Week 48 followed by an End-of-LTE Therapy visit at Week 52, and then proceed to the LTE Therapy Follow-up Period (Week 56 through Week 64). Refer to Section 8.1.4.2 for additional dosing details in LTE Therapy.

Note: Subjects who already started treatment in the double-blind LTE Therapy will continue to receive KHK4083 or placebo during LTE Therapy. If their UC worsens or flares up to Week 28, they may transition to OLE therapy.

Subjects who did not qualify were to have received no further treatment and entered the Induction Therapy Follow-up Period.

6.1.3 Open-label Extension Therapy: Week 12 (First Dose) to Week 52

Subjects who complete double-blind Induction Therapy (i.e., at least five of six treatments) are eligible to enter OLE Therapy (refer to Section 7.4 for specific eligibility criteria).

All subjects who qualify will be given two options:

- 1) To receive no further treatment and proceed directly to the Induction Therapy Follow-up Period (Week 16 through Week 26); or
- 2) To receive 10 treatments of open-label KHK4083 (at the same dose administered to that subject during Induction Therapy) as maintenance therapy. Each subject will receive one IV infusion every 4 weeks from Week 12 to Week 48 followed by an End-of-OLE Therapy visit at Week 52, and then proceed to the OLE Therapy Follow-up Period (Week 56 through Week 64). Refer to Section 8.1.4.2 for additional dosing details in OLE Therapy.

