6.1.4 Transitioning from the Long-term Extension to the Open-label Extension

Subjects participating in the double-blind LTE who experience a clinical worsening or a flare of disease up to Week 28, as defined by the Investigator, may transition to the OLE. Subjects will maintain the same visit schedule, e.g., a subject who completed a Week 20 visit in the LTE and transitions to the OLE at Week 24 will have an OLE Week 24 visit. However, for the first two open-label doses in the OLE, additional safety monitoring will include ECGs and post-infusion monitoring as performed for the OLE Week 12 and Week 16 visits, respectively.

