- b: Cohort 4 will receive the recommended dose (1.0, 3.0 or 10 mg/kg) determined from safety assessments of Cohorts 1 - 3 in Part A.
- c: Subjects who complete Induction Therapy, have evaluable total Mayo Clinic scores, and have met the criteria for a clinical response or mucosal healing will have the option to continue in LTE Therapy. Subjects who qualify will receive 10 additional treatments (one IV infusion every 4 weeks) of KHK4083 (at the same dose administered to that subject during Induction Therapy) or placebo. (Note: Subjects administered placebo during Induction Therapy will receive placebo during LTE Therapy).
- C=cohort; LTE=long-term extension; MAD= multiple ascending dose.

[figure not shown]
	Forms			
	Title	Statistical Analysis Plan Template		
	Code	Version	Effective Date	Page
	FRM_ST03_032	01	23 Apr 2015	15 of 53

Figure 2 Study Design Diagram in Protocol Amendment 2

Non-completer (NC) - Subject did not complete Induction Therapy

- a: **For those subjects who enrolled under Amendment #1-** Subjects will be in the study for a total of up to 64 weeks. The double blind treatment period includes Induction Therapy (12 weeks) and LTE therapy (40 weeks). A post treatment follow-up period will be conducted at either Weeks 16, 20 and 26 for subjects who only receive Induction Therapy or at weeks 56, 60 and 64 for subjects who receive both induction and LTE Therapies
- b: Cohort 4 will receive the recommended dose (1.0, 3.0, or 10 mg/kg) determined from safety assessments of Cohorts 1 - 3 in Part A.
- c: Endoscopic Responders (ER) include subjects who met the criteria for clinical response at Week 12 and non-responders (NR) includes subjects who did not meet the criteria of a clinical response at Week 12.
- d: **For those subjects who enroll under Amendment #2-**All subjects who complete the induction period, i.e., (received at least of 5 of the 6 doses of double-blind therapy and have Week 12 sigmoidoscopy results from the central reader) and are eligible to continue on in the study have the option to enter the OLE therapy part of the trial and receive 10 additional treatments of KHK4083 once every 4 weeks from week 12 through week 48 at the same dose used in the cohort that they were enrolled in.

C=cohort; IV=intravenous; LTE=long-term extension; OLE=Open-label Extension; MAD=multiple ascending dose; R=randomization.

	Forms			
	Title	Statistical Analysis Plan Template		
	Code	Version	Effective Date	Page
	FRM_ST03_032	01	23 Apr 2015	16 of 53

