4.1 General

General descriptive statistics for continuous variables include the n (number of observed values), the mean, standard deviation, median, minimum, and maximum values. For categorical variables, the number and percentage of subjects with a specific level of the variable will be presented. The percentage will be calculated using the subjects with a reported value. Counts of missing subjects will be identified for variables that had one or more subjects with a missing result. Descriptive statistics will be presented by treatment Cohort (KHK4083 dose levels; combined KHK4083; and placebo) and by visit.

Unless there are any notes, the following rules will be applied for all tables and figures;

- Data from placebo subjects in each Cohort will be combined, not depending on treatment period (Double-Blind Induction Therapy, Long-Term Extension Therapy, Open-Label Extension Therapy, or Follow-up).
- In the case that Screening or Baseline is necessary in the tables and figures related to LTE Therapy Period, OLE Therapy Period, or Follow-up Period, the data at Screening or Baseline will be used or displayed.
- Double-Blind Therapy Period will be defined as the period including both Double-Blind Induction Therapy Period and LTE Therapy Period.
- When “Week xx” (xx: number) is necessary, “Week xx” displayed on CRF will be used or displayed.

To explain how data are summarized, the figure showing the relationship between period and dose of Investigational Product is displayed in Figure 3 and the table defining the category is displayed in Table 2.

[figure not shown]
	Forms			
	Title	Statistical Analysis Plan Template		
	Code	Version	Effective Date	Page
	FRM_ST03_032	01	23 Apr 2015	20 of 53

Figure 3 Relationship between Period and Dose of Investigational Product

Subjects who do not move to OLE/LTE Therapy

Subjects who move to OLE/LTE Therapy

[figure not shown]

Table 2 Category in Tables and Figures

	4083 Randomized				Placebo Randomized			
	Cohort 1	Cohort 2	Cohort 3	Cohort 4	Cohort 1	Cohort 2	Cohort 3	Cohort 4
Summary Pattern	Category In Tables and Figures							
Double-Blind Induction Therapy Period	1.0 mg/kg	3.0 mg/kg	10 mg/kg	1.0, 3.0 or 10 mg/kg	Placebo			
Double-Blind Therapy Period ¹⁾								
Double-Blind Therapy Period and Double-Blind Therapy Follow-up Period ²⁾								
LTE Therapy Period								
LTE Therapy Period and Double-Blind Therapy Follow-up Period	1.0 mg/kg	3.0 mg/kg	10 mg/kg	1.0, 3.0 or 10 mg/kg	Placebo ³⁾			

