 - Change from baseline in corticosteroid (glucocorticoid) dosages at Week 16 through LTE Therapy Follow-up Period = Glucocorticoid dosages at Week 16 through LTE Therapy Follow-up Period - Baseline glucocorticoid dosages
 - Change from baseline in corticosteroid (glucocorticoid) dosages at Week 16 through OLE Therapy Follow-up Period = Glucocorticoid dosages at Week 16 through OLE Therapy Follow-up Period - Baseline glucocorticoid dosages
- Duration of glucocorticoid-free treatment will be defined as the duration that no glucocorticoid listed in Section 9.3 is used from Week 16 through Follow-up 3.
 - Duration of glucocorticoid-free treatment (days) = Date of first glucocorticoid after Week 16 visit - Date of Week 16 visit
 - If the subject received glucocorticoid on the date of Week 16 visit, the duration of glucocorticoid-free treatment for the subject is 0.

A comparison between treatments (each KHK4083 dose level versus placebo) will be performed using an ANCOVA model with changes from Baseline in UCEIS, total Mayo Clinic score and partial Mayo Clinic score at Week 52 during Double-Blind Therapy Period as dependent variables, treatment as fixed effect and baseline value as covariate. The number of subjects and the number of subjects considered in the model will be provided by treatment. The adjusted means for treatments (least squares means) and the relative 95% CIs will be presented. The difference between the adjusted means for each treatment groups from placebo (Difference in Least Squares Mean from Placebo) will be calculated with the relative 95% CI and p-value. If ANCOVA cannot be applied

	Forms			
	Title	Statistical Analysis Plan Template		
	Code	Version	Effective Date	Page
	FRM_ST03_032	01	23 Apr 2015	33 of 53

due to the issue that the parameters cannot be estimated appropriately, these analyses using ANCOVA for Week 52 will not be applied.

Means with SDs for the efficacy variables (mMES, UCEIS, total Mayo score and partial Mayo score) at all visits will be performed graphically by each treatment (e.g. Placebo, 1.0 mg/kg, 3.0 mg/kg, or 10 mg/kg) and by Double-Blind Therapy Period and OLE Therapy Period. For partial Mayo score, Means with SDs as all visits will be performed graphically by “Double-Blind Therapy Period and Double-Blind Therapy Follow-up Period” and “OLE Therapy Period and OLE Therapy Follow-up Period”. Mean changes from Baseline will also be performed in the same manner.

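### The Week 52 double-blind ANCOVA in SAP 7.3 compares KHK4083 with placebo only among subjects selected on post-randomisation outcomes, so its difference, interval and p-value carry a bias of unknown direction.

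*SAP*

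**What the plan says.** SAP 7.3 plans an ANCOVA of "changes from Baseline in UCEIS, total Mayo Clinic score and partial Mayo Clinic score at Week 52 during Double-Blind Therapy Period", with treatment as fixed effect and the Week 0 value as covariate. It reports least squares means, the difference of each dose from placebo, a 95% confidence interval and a p-value (Tables 14.2-3.8.1 to 14.2-3.8.3). The model is dropped only if its parameters cannot be estimated. No caveat about who contributes data is given.

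Who contributes follows from these provisions:

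- **Period.** SAP 4.1: "Double-Blind Therapy Period will be defined as the period including both Double-Blind Induction Therapy Period and LTE Therapy Period". Subjects treated in induction only are followed to Week 26 (Protocol 6.1), so Week 52 data under double-blind treatment come only from the LTE.
- **Week 12 outcome.** Protocol 6.1.2: subjects who completed at least five of six treatments and "had a clinical response or mucosal healing were eligible to continue in double-blind LTE Therapy".
- **Choice.** Those who qualified could decline and go to follow-up (Protocol 6.1.2).
- **Calendar time.** Protocol 6.1.2: "The LTE is only active for subjects who entered it prior to approval of Amendment 2".
- **Exit.** Protocol 6.1.4: LTE subjects "who experience a clinical worsening or a flare of disease up to Week 28", as judged by the investigator, may move to the OLE. SAP 4.1 (Table 2) summarises the OLE separately.
- **No new randomisation.** SAP 3.1, Figure 1, footnote c: "Subjects administered placebo during Induction Therapy will receive placebo during LTE Therapy".
- **Missing data.** Protocol 12.6 leaves missing values missing.

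**The concern.** Response or healing at Week 12, and worsening enough to leave the LTE, both occur after randomisation, and both can be changed by treatment. Once the analysis is restricted to subjects who passed both, the arms are no longer comparable by design. The Week 0 covariate does not restore this, because the selection acts on what happened after Week 0.

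The output nevertheless has the same form as the randomised Week 12 analysis: a difference from placebo with an interval and p-value. SAP 1 says the planned analyses will go into regulatory submissions and/or manuscripts. A reader could take the Week 52 contrast as evidence for or against a maintained effect, and nothing in the table would show which way it is biased.

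**Working it through.** **The plan's own figures.** Protocol 12.3.4 gives 60 randomised for 51 evaluable at 15% dropout: 51/0.85 = 60. The recommended dose has 9 + 18 = 27 subjects and placebo has 3 × 3 + 6 = 15. These reproduce. No effect size, SD, qualification rate, flare rate or Week 52 sample size is stated, so every input below is an assumption.

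**How many subjects remain.** Formula: randomised × 0.85 × Week 12 qualification rate × (1 − flare exit rate).

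| Qualify, placebo / drug | Flare exit | Placebo of 15 | Recommended dose of 27 | Part A only: placebo of 9 | Part A only: one dose of 9 |
|---|---|---|---|---|---|
| 20% / 40% | 0% | 2.6 | 9.2 | 1.5 | 3.1 |
| 30% / 50% | 20% | 3.1 | 9.2 | 1.8 | 3.1 |
| 40% / 60% | 30% | 3.6 | 9.6 | 2.1 | 3.2 |

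The left pair of counts treats the LTE as open to all cohorts. The documents do not say which cohorts reached Week 12 before Amendment 2 was approved.

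**Precision.** The half-width of the 95% interval is 1.96 × SD × √(1/n₁ + 1/n₂), with an assumed total Mayo SD of 2.5:

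- 4 against 11: 1.96 × 2.5 × √(1/4 + 1/11) = 2.9 points; power for a 1.5-point difference is 18%.
- 2 against 4: 1.96 × 2.5 × √(1/2 + 1/4) = 4.2 points; power is 10%.

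**Direction of bias.** Simulation with 1,000,000 subjects per arm. Change in total Mayo has SD 2.5 and placebo mean -1.5. A subject enters the LTE if the Week 12 change is -3 or lower, and leaves if Week 28 is at least 3 points worse than Week 12. Within-subject correlation ρ is 0.3, 0.5 or 0.7. The figure is the mean difference at Week 52, drug minus placebo, so negative favours KHK4083.

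| Scenario | True difference, all randomised | LTE stayers, ρ = 0.3 | ρ = 0.5 | ρ = 0.7 |
|---|---|---|---|---|
| Same effect in everyone, maintained | -1.5 | -1.10 | -0.89 | -0.74 |
| Same average effect, confined to 40% | -1.5 | -2.07 | -1.72 | -1.42 |
| Same average effect, confined to 25% | -1.5 | -3.00 | -2.55 | -2.18 |
| -1.5 at Week 12, gone by Week 52 | 0 | +0.29 | +0.45 | +0.62 |
| No effect at any time | 0 | about 0 | about 0 | about 0 |

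The first row is attenuation: (1.5 − 1.10)/1.5 = 27% to (1.5 − 0.74)/1.5 = 51% of the effect is lost. The next two rows are mostly exaggeration, up to twice the true value. In the fourth, a true zero appears as an advantage for placebo.

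The simulation is simpler than the protocol. It omits entry through mucosal healing, replaces the investigator's optional transfer with a fixed rule, and covers total Mayo only. It shows that the sign of the bias depends on unknowns. It does not estimate the bias in this trial.

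**The case against.** The strongest reply is that little rests on this analysis. Protocol 12.3.5 calls all analyses descriptive or exploratory, SAP 4.1 says hypothesis testing will not be carried out, and SAP 4.5 bases proof of concept on Week 12 data. The exploratory objectives compare Week 52 with Week 0, and Protocol 10.3 defines the endpoints for subjects who received both phases, so the restricted population is stated. SAP 5.1 reports how many moved from LTE to OLE, and SAP 7.3 gives the number in each model. For partial Mayo, a repeated-measures model also uses data from subjects who never entered the LTE. Durable response at Weeks 12 and 52 is already planned. If treatment had no effect at any time, the simulated contrast is centred on zero.

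Most of this stands, and it limits severity. It does not make the contrast a treatment effect. An objective framed against Week 0 gives no reason to print a difference from placebo. The repeated-measures model helps only partial Mayo, and only if data are missing at random; UCEIS and total Mayo have no counterpart. The durable-response denominator is unsettled, since SAP 4.1 uses subjects with a reported value and SAP 4.4 uses the treatment or cohort group.

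A reader might infer that the analysis specifically hides a maintained effect, shrinking it by a quarter to a half, because the placebo subjects left are spontaneous remitters. The documents do not support that. The shrinkage needs an equal effect in every subject. LTE entry required response or healing, not remission. Stable background UC treatment is allowed (Protocol 8.5). Transfer to the OLE is optional and ends at Week 28, so later flares are not removed by that route.

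**Conclusion.** The point holds with the direction left open. The Week 52 double-blind contrasts for UCEIS, total Mayo and partial Mayo are not randomised comparisons. They can hide or exaggerate a maintained effect, and can turn against KHK4083 when an effect has faded. Their intervals and p-values therefore do not describe the treatment effect at Week 52.

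That conclusion rests on the documents alone. The sizes do not: -0.74 to -3.00 for a true -1.5, and about two to four placebo subjects, depend on the stated assumptions. With so few subjects, imprecision of roughly 3 to 4 points would be at least as serious as the bias in most scenarios. The Week 12 primary analysis is not touched by this selection. The change is worth making because it is cheap, but the trial's main conclusion does not depend on it.

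**What to change.** 1. In SAP 7.3 and Tables 14.2-3.8.1 to 14.2-3.8.3, show Week 52 LTE scores descriptively by arm, labelled as conditional on LTE entry. Remove the difference from placebo, its 95% confidence interval and the p-value.
2. Protocol 12.3.3 plans linear-model comparisons for continuous exploratory variables, so record the departure under Protocol 12.8.
3. For the durable clinical response already planned, fix the double-blind denominator as all subjects randomised who were subject to the Amendment 1 LTE rules, including those who withdrew before Week 12. Restricting it to subjects who reached Week 12 would bring back a smaller selection. The full analysis set would too, since it requires a post-treatment mMES.
4. Count non-entry to the LTE, transition to the OLE, discontinuation or a missing Week 52 as not durable. Show the number of subjects by arm at each step.

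The cost is SAP wording and one responder summary from data already collected. Three exploratory tables lose their placebo contrasts. The responder table will be imprecise: with all 27 and 15 subjects, Fisher's exact test has about 28% to 29% power for assumed rates of 30% against 8%, or 42% against 19%; with 9 and 9 it has 6% to 9%. It should be read as description.

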12.3.2 Secondary Efficacy Analyses

The secondary efficacy variables for all subjects (i.e., recommended dose or any other dose level in Parts A and B of Induction Therapy) are as follows:

- The percentages of subjects with at least a 1-point improvement in their mMES from Baseline (Week 0) to Week 12.
- The percentages of subjects with at least a 1-point improvement in their modified Baron endoscopic score from Baseline (Week 0) to Week 12.
- The mean change in UCEIS (0 to 8) and subscores from Baseline (Week 0) to Week 12.
- The percentage of subjects with a mucosal healing (the mMES \leq 1) at Week 12.
- The change from Baseline (Week 0) in total Mayo Clinic score (0 to 12) at Week 12.
- The change from Baseline (Week 0) in partial Mayo Clinic scores (0 to 9; without sigmoidoscopy) at Weeks 2, 4, 6, 8, 10, and 12.

- The percentages of clinical response (the change from Baseline in the total Mayo Clinic score ≤ -3 and the percentage change from Baseline in the total Mayo Clinic score $\leq -30\%$ to Week 12, with an accompanying decrease in the rectal bleeding subscore of at least 1 point or an absolute rectal bleeding subscore of ≤ 1).
- The percentages of clinical remission (a total Mayo Clinic score ≤ 2 and no subscores > 1) at Week 12.

Treatment (each KHK4083 dose level versus placebo) comparisons by cohort will be performed with the linear model for all secondary efficacy analyses of continuous variables.

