7.2 Analysis of secondary efficacy endpoints

The secondary efficacy variables for all subjects (i.e., recommended dose or any other dose level in Parts A and B of Induction Therapy) are listed in the following table.

Efficacy Variables	Definition
Improvement in the Mucosa (Measured by modified Mayo endoscopy subscore [mMES]) (Week 12)	Percentage of subjects with at least a 1-point improvement in their mMES (0 to 3) from Baseline (Week 0) to Week 12.
Improvement in the Mucosa (Measured by modified Baron scoring system) (Week 12)	Percentage of subjects with at least a 1-point improvement in their modified Baron endoscopic score (5-point scale) from Baseline (Week 0) to Week 12.
Improvement in the Mucosa (Measured by Ulcerative Colitis Endoscopic Index of Severity [UCEIS]) (Week 12)	A mean change in the UCEIS (scores from 0 to 8, based on findings of vascular pattern, bleeding, and erosions/ulcers) from Baseline (Week 0) to Week 12.
Mucosal Healing (Week 12)	The percentage of subjects with mMES of 0 or 1 at Week 12.
Clinical Improvement (Week 12)	Mean change from Baseline (Week 0) at Week 12, in the total Mayo Clinic score (0 to 12).
Clinical Improvement (Weeks 2, 4, 6, 8, 10, and 12)	Mean changes from Baseline (Week 0) in the partial (excludes endoscopy subscores) Mayo Clinic score (0 to 10).
Clinical Response (Week 12)	A reduction in the total Mayo Clinic score of at least 3 points and a decrease of at least 30% from Baseline (Week 0) to Week 12, and a reduction in the rectal bleeding subscale of at least 1 point from Baseline (Week 0) to Week 12 or an absolute rectal bleeding score of 0 or 1 at Week 12.
Clinical Remission (Week 12)	A total Mayo Clinic score of ≤ 2 and no subscores > 1 .

All secondary efficacy variables will be summarized by treatments (each KHK4083 dose level and placebo). Change from Baseline in UCEIS, total Mayo Clinic score as well as Baseline and Week 12 will be summarized by treatments. Partial Mayo Clinic scores and changes from Baseline will be summarized from Baseline to Week 12 by treatments. Summaries statistics and 95% CI will be presented and estimated as described in section 7.1 of this SAP.

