A comparison between treatments (each KHK4083 dose level versus placebo) will be performed using an ANCOVA model with changes from Baseline in UCEIS, total Mayo Clinic score and partial Mayo Clinic score at Week 12 as dependent variables, treatment as fixed effect and baseline value as covariate. The number of subjects and the number of subjects considered in the model will be provided by treatment. The adjusted means for treatments (least squares means) and the relative 95% CIs will be presented. The difference between the adjusted means for each treatment groups from placebo (Difference in Least Squares Mean from Placebo) will be calculated with the relative 95% CI and p-value. Least squares means with 95% CIs and differences in least squares mean from placebo with 95% CIs will be graphically presented.

	Forms			
	Title	Statistical Analysis Plan Template		
	Code	Version	Effective Date	Page
	FRM_ST03_032	01	23 Apr 2015	31 of 53

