To take into consideration about the repeat measurements in partial Mayo Clinic score, an analysis using a Mixed Model for Repeated Measures (MMRM) will be performed. A comparison between treatments (each KHK4083 dose level versus placebo) will be performed using a MMRM with the change from baseline in partial Mayo Clinic scores during Double-Blind Therapy Period and Double-Blind Therapy Follow-up Period as dependent variable, treatment as fixed effect and baseline value as covariate, and visit as random effects. The interaction between treatment and visit also will be included. An unstructured covariance matrix will be considered and the Kenward-Roger adjustment will be used for the degrees of freedom. In the case that the unstructured covariance matrix cannot be used, a compound symmetry will be used as the covariance matrix instead of the unstructured one. The number of subjects, the number of subjects considered in the model and the number of observations considered in the model will be provided by treatments. The adjusted means for treatments (least squares means) at each visit and the relative 95% CIs will be presented. The differences between the adjusted means for treatments from placebo (Difference in Least Squares Mean from Placebo) at each visit will be calculated with the relative 95% CIs and p-values. If MMRM cannot be applied due to the issue that the parameters cannot be estimated appropriately, the structure of covariance matrix will be changed to compound symmetry. If MMRM cannot be applied by using the covariance matrix of compound symmetry, this analysis using MMRM will not be applied.

SAS® code

```
proc mixed data=dat001 ORDER=DATA;
  class visit tmt;
  model chg=tmt visit baseline tmt*visit /solution ddfm=kr;
  repeated visit / type=un subject= subjectj;
  lsmeans tmt*visit / slice=tmt pdiff diff alpha=0.05 cl;
  lsmeans tmt / pdiff diff alpha=0.05 cl;
run;
```

For the following scores, to show changes in score during the study, those scores will be summarized by treatments.

- Subscores of Mayo Clinic Score other than mMES: “Stool Frequency”, “Rectal Bleeding”, and “Physician’s Global Assessment”
- Modified Baron Endoscopic Score
- Subscores of UCEIS: “Vascular pattern”, “Bleeding”, and “Erosions and ulcers”

	Forms			
	Title	Statistical Analysis Plan Template		
	Code	Version	Effective Date	Page
	FRM_ST03_032	01	23 Apr 2015	34 of 53

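### The single partial Mayo MMRM in SAP 7.3 runs across mutually exclusive tracks after Week 12 and very probably ends on compound symmetry, so the Weeks 2-10 secondary comparisons need their own Weeks 2-12 model

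*SAP*

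**What the plan says.** SAP 7.3 models "change from baseline in partial Mayo Clinic scores during Double-Blind Therapy Period and Double-Blind Therapy Follow-up Period as dependent variable", with treatment, visit, their interaction and baseline. SAP 4.1 (Table 2 footnotes) defines the first period as induction plus LTE, and the second as the follow-up after either. The covariance is unstructured with Kenward-Roger. If that is unusable, "a compound symmetry will be used as the covariance matrix instead of the unstructured one"; if that also fails, the MMRM is dropped. The code also contains `"lsmeans tmt / pdiff diff alpha=0.05 cl"`, an all-visit treatment contrast that the text does not mention.

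On visit labels, SAP 4.1 says that where a week number is needed, the one "displayed on CRF will be used or displayed".

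Protocol 12.3.2 lists as secondary the change "in partial Mayo Clinic scores (0 to 9; without sigmoidoscopy) at Weeks 2, 4, 6, 8, 10, and 12" and promises that treatment "comparisons by cohort will be performed with the linear model for all secondary efficacy analyses of continuous variables". SAP 7.2 supplies an ANCOVA with "partial Mayo Clinic score at Week 12 as dependent variables, treatment as fixed effect and baseline value as covariate", so at Week 12 only.

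**The concern.** Protocol 6.1 sends each subject down one path after Week 12. Those who receive induction only are seen off drug at Weeks 16, 20 and 26. LTE subjects are seen at Weeks 16 to 52 and then at 56, 60 and 64. OLE visits are outside this model. An unstructured matrix needs every pair of visits to be observed together in some subjects, and here some pairs may never be. Most of the rest depend on the LTE group. Protocol 6.1.2 limits that group to subjects with Week 12 response or healing who entered before Amendment 2 was approved.

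If the unstructured fit fails, the only other structure named assumes one variance and one correlation from Week 2 to Week 64. At stake are the between-arm comparisons at Weeks 2-10: the protocol promises them for a secondary variable, and no other SAP model supplies them.

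Contrasts after Week 12 also lose their randomised basis. LTE entry depends on outcome, worsening LTE subjects may move to the OLE up to Week 28 (protocol 6.1.4), UC medication may change (8.5), and otherwise prohibited treatments are allowed in follow-up (8.5.1).

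**Working it through.** **The plan's own figure.** None is given for the MMRM. The sample size reproduces: 51/(1 - 0.15) = 60 = 3×12 + 24, split 27 at the recommended dose, 15 placebo and 9 at each other dose. The documents give no SDs and no LTE count.

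**Inputs.** Induction Weeks 2, 4, 6, 8, 10, 12 (SAP 3.4.2); LTE Weeks 16-52 every four weeks, 10 visits (SAP 7.3); follow-up Weeks 16, 20, 26 or 56, 60, 64 (protocol 6.1).

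**Parameter counts.** An unstructured matrix on p visits has p(p+1)/2 parameters. Three ways of coding visit are possible: (A) week labels shared by the tracks; (B) track-specific labels, as the CRF page names in SAP 5.1 suggest; (C) Follow-up 1-3 as common visits.

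| Coding | Visits | Parameters | Empty | LTE only | Off-drug follow-up only | Both tracks |
|---|---|---|---|---|---|---|
| A | 20 | 210 | 11 | 154 | 9 | 36 |
| B | 22 | 253 | 39 | 169 | 24 | 21 |
| C | 19 | 190 | 0 | 145 | 0 | 45 |
| Weeks 2-12 only | 6 | 21 | 0 | - | - | - |

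- A: empty = Week 26 paired with Weeks 24, 28, 32, 36, 40, 44, 48, 52, 56, 60 and 64 = 11. LTE only = 11×12/2 + 11×8 = 154. Follow-up only = 1 + 8 = 9. Both = 8×9/2 = 36.
- B: empty = 3×13 = 39. LTE only = 13×14/2 + 13×6 = 169. Follow-up only = 3×4/2 + 3×6 = 24. Both = 6×7/2 = 21.
- C: LTE only = 10×11/2 + 10×9 = 145. Both = 9×10/2 = 45.

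The information matrix for the covariance parameters has rank 199 of 210 under A, 214 of 253 under B and 190 of 190 under C.

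**LTE subjects needed under A or B, leaving the empty pairs aside.** The LTE-only visits need as many residual degrees of freedom as there are such visits, after fitting arm means and the visits that other subjects also inform. The minimum is arms + 8 + 11 (A) or arms + 6 + 13 (B), so arms + 19 either way: 21, 22 or 23 for two, three or four arms, all with data through Week 64.

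| Assumed source of LTE entrants | Subjects | Arms | Minimum | Share needed |
|---|---|---|---|---|
| Cohort 1 | 12 | 2 | 21 | more than all |
| Cohorts 1-2 | 24 | 3 | 22 | 92% |
| Cohorts 1-3 | 36 | 4 | 23 | 64% |
| Cohorts 1-4 | 60 | 4 | 23 | 38% |

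With 15% dropout and an assumed 30-70% qualifying, Cohort 1 gives about 3 entrants at the low end (12×0.85×0.3) and Cohorts 1-3 about 21 at the high end (36×0.85×0.7). Only if all four cohorts fed the LTE could the minimum be reached (60×0.85×0.7 = 36; at 30%, 15).

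**Cost of compound symmetry (assumed SDs, linear over six visits, complete Weeks 2-12 data).** The ratio of fitted to correct SE at a visit is √(mean variance)/SD at that visit.

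- SD 1.3 to 2.3: √(20.14/6) = 1.832; Week 2: 1.832/1.3 = 1.41; Week 12: 1.832/2.3 = 0.80.
- SD 1.6 to 2.2: √(21.91/6) = 1.911; Week 2: 1.911/1.6 = 1.19; Week 12: 1.911/2.2 = 0.87.
- Constant SD: 1.00 throughout.

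**Check of the remedy by simulation.** Assumptions: arms 15/9/9/27, contrast 27 against 15, 15% monotone dropout, correlation 0.6 exchangeable or 0.8^lag, 700 trials per case, approximate rather than Kenward-Roger degrees of freedom. The Weeks 2-12 unstructured MMRM had 95% CI coverage of 0.934-0.961 over all visits and cases. Compound symmetry on the same data covered at Week 12 in 0.863-0.891 (SD 1.3-2.3), 0.907-0.910 (SD 1.6-2.2) and 0.954-0.956 (constant SD).

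**The all-visit contrast.** If every arm had data at every visit, equal weighting would put 14/20 = 70% (A) or 16/22 = 73% (B) of `lsmeans tmt` after Week 12. For an arm with no LTE data it is not estimable.

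**The case against.** A reader might infer that the unstructured matrix is unidentifiable at any sample size. The documents do not support that without a condition. Both protocol schedules head the off-drug visits Follow-up 1, 2 and 3, SAP 7.3 uses Follow-up 3 as a timepoint, and the coding of visit in the analysis dataset is not given. Coding C has no empty pairs. What stands is that C equates off-drug Weeks 16, 20 and 26 with Weeks 56, 60 and 64, is not what the SAP 4.1 week-label rule produces, and still leaves 145 of 190 parameters to the LTE group.

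A reader might also infer that the MMRM should simply stop at Week 12. Protocol 12.3.3 promises linear-model comparisons for continuous exploratory variables, and these include partial Mayo at Weeks 16-52 and 56-64. Removing those visits would leave only the Week 52 ANCOVA after Week 12, with no between-arm model at Weeks 16-48 and 56-64. This objection stands and shapes the fix.

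Finally, the SAP foresees estimation failure and orders its fallbacks, and the harm shown rests on assumed SDs in a six-visit model. That is so, but the ordering offers only compound symmetry before dropping the analysis. On description, SAP 7.2 already provides that "Partial Mayo Clinic scores and changes from Baseline will be summarized from Baseline to Week 12 by treatments", with 95% CIs. That gives per-arm estimates, not the promised comparison.

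**Conclusion.** The concern holds as a modest point about model choice. Under week labels or track-specific labels the specified covariance is not identifiable. Under common follow-up labels it is identifiable in principle but leans on a small, responder-selected, closed group of unstated size. The plan therefore very probably ends on compound symmetry or on no model, and the Weeks 2-10 secondary comparisons go with it. If SD rises over induction as assumed, Week 12 standard errors are 13-20% too small and Week 2 standard errors 19-41% too large; if SD is constant there is no error.

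It would be wrong to infer that the empty pairs themselves bias Weeks 2-12; they matter because they trigger the fallback. Nor do the main conclusions depend on this table. It is exploratory (Table 14.2-3.8.4), SAP 4.1 plans no formal testing, and the primary mMES ANCOVA, the Week 12 partial Mayo ANCOVA and the Week 12 proof-of-concept tables (SAP 9.4.1) do not use it.

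**What to change.** 1. Add a separate MMRM on Weeks 2-12 with unstructured covariance, and name it as the between-arm model for the Weeks 2-10 secondary variable in protocol 12.3.2.
2. Replace the compound-symmetry fallback with a heterogeneous-variance structure, such as heterogeneous Toeplitz or heterogeneous AR(1).
3. Limit `lsmeans tmt` to induction visits, or remove it.
4. After Week 12, either keep a separate exploratory LTE model, labelled as a non-randomised comparison among responders, or report those visits descriptively and record that as a departure from protocol 12.3.3.

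The cost is SAP wording and one smaller model, with no new data. Under the descriptive option the sponsor also gives up MMRM p-values after Week 12.
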